Medication. Hypertensive patients will be treated with distinctively colored, *odored and flavored* gelatine capsules (Capsuline, Inc, Pompano Beach, FL) containing 12.5 mg (generic version, available from the Strong Memorial Hospital Research Pharmacy). The “placebo” will be a capsule containing 12.5 mg of an inert substance with the same characteristics as the active drug capsules. Capsules will be packaged in a blister strip of single application packets by the Investigational Drug Studies program in the Strong Memorial Hospital Research Pharmacy. Preparation of the sequence of medication would be done from coded patient numbers and would depend upon the schedule of reinforcement that was being used. For example, if one were imposing a 25% reinforcement schedule (only one fourth of the packets of capsules containing active drug), a random sequence would be constituted with the proviso that the patient would receive no more than two doses of consecutive placebo capsules. Randomization will be performed by the research pharmacy in blocks of eight. Allocation concealment will be guaranteed, since only the research pharmacist will be aware of group distribution and all other members of the research team will be blinded. He will provide the research nurse with the pre-labeled packages.

Length of study: 8 weeks for those subjects that complete the full set of procedures. For those subjects who relapse early, or whose blood pressure does not remit (10-point decrease for a period of 5 days) prior to the Exp 1 phase, the minimal period in the study is 3 weeks.

Exp 1: Baseline Period: 2 weeks after a screening physical examination that will be performed within one week of admission. ; Experimental Phase: 2 weeks (or less for subjects' whose mild hypertension relapses). Therefore, maximal possible period receiving carvedilol: 4 weeks.

Exp 2: 4 weeks. In this experiment subjects either receive placebo or no treatment. We expect the latter group to relapse after a few days. Those receiving placebo are hypothesized to relapse later, and we are assuming that will relapse before 4 weeks on placebo. However, if we find that there are subjects that after 4 weeks have not relapsed, we plan to continue the administration of the placebo until they relapse (beyond the 4 weeks). Because we believe that this will occur rarely, for practical reasons we will state in the consent form that this period may last “up to 4 weeks”.

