The choice of the β/α blocker for this study was based on:

a) targets receptors of the peripheral nervous system (PNS); it is a non-selective β -adrenergic blocking agent with alpha-1 blocking activity. It is approved for use in hypertension as well as heart failure. Other hypotensive drugs could have been chosen, however, their primary target is not “directly” aimed at the PNS or CNS. We are aware that ACE inhibitors decrease catecholamines, and angiotensin receptor blockers decrease vasopressin, however, for this initial study we chose a drug that is mostly associated to the sympathetic system. We believe that this will provide the best chances of success. Future studies will include alternative drugs.

b) Carvedilol has no adverse effect on glycemic control, and is the preferred β blocking agent for patients that have diabetes (as some of ours may).

c) We have preliminary published data (28) that strongly suggests the effectiveness of our conditioning paradigm in the pharmacotherapy of hypertension using a similar β blocker.

d) can be administered two times a day, leading to an enhanced number of “learned” exposures to the stimulus, and this regimen guarantees that subjects in groups that receive only one active drug

administration out of 4 will take adequate daily amounts of that will prevent them from the undesired rebound side effects of this medication that could occur if they were to have 3 days with no active drug.

Subjects will be started on the lowest recommended starting dose of 25 mg daily in 2 fractionated doses, which is reasonable given their level of hypertension (33,34). Once a reasonable blood pressure drop is achieved, they will be randomized to four experimental groups, as described in the methods section.

Potential participants will be informed that the purpose of the study is to determine if their blood pressure could be brought under control using lower amounts of medication and that, in the course of the study, the amount of medication they receive may be reduced. The medical staff with whom the patient comes in contact will not know if or when this occurs. Measurement of blood pressure during the study will be performed by the patients themselves, who will be instructed in the use of automated BP monitors (HEM-711AC, Omron Healthcare Inc., Bannockburn, IL) which will be provided. Subjects will obtain measurements twice (one after the other) in the AM and twice (one after the other) in the PM always at the same time of day.

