It is possible that the therapeutic effects of a partial schedule of pharmacologic reinforcement (and, thus, a reduced amount of active drug) will be indistinguishable from a continuous (standard) regimen of pharmacotherapy. That outcome, however, is not critical for evaluating the role of conditioning in pharmacotherapies simply because these groups would have received different amounts of drug. Specifically, *it is hypothesized that patients treated under a noncontinuous schedule of medication will be less likely to show a recurrence of symptoms ("relapse") than patients treated with that same amount of drug administered under a continuous schedule of reinforcement.*

On the first visit, each potential subject will undergo a brief physical examination to record the medical history, sign an informed consent form, and receive instruction in the use of a blood pressure monitor. A strip of medication packets will be supplied at each clinic visit and will be taken by the subject at home, 2

times a day for the duration of the study.. The subject will return to the study center once a week or within 14 days of the drug dispensing cycle; this will allow flexibility for those with travel or work schedule challenges. The study coordinator will email or call to check on safety of the subject in the interim of a weekly clinic visit. Each drug card contains 15 days of study drug to ensure continual dosing in the event a weekly visit is missed. Packets containing medication will be dispensed by code so the patient and the physician will be blinded as to the nature of the medication. To consider the possibility that conditioning might be influenced by immediate stressful life experiences in these patients, we will examine this relationship using two measures of psychological distress administered at weekly intervals: the Hassles Scale, a frequently-used measure of daily stressors or “hassles” and the Impact of Events Scale (IES) (31).

The protocol for Experiment 1 is shown in Table 1. During a baseline period (of a maximum of 15 days), all patients will be treated BID with 12.5 mg. Those who satisfy the criterion of a 10-point decrease in blood pressure for a period of 5 days will be assigned randomly to experimental groups.

During the 15-day experimental period, the patients will be treated as follows:

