Patients in a **Standard Therapy Group** will continue to receive 100% of the dose of medication on the same reinforcement schedule (100%) as they received during the baseline (maintenance) period. (12.5 mg) would be taken 2 times daily for 15 additional days. This is a continuation of their standard pharmacotherapeutic maintenance regimen and constitutes one control group.

The **Partial Reinforcement Group** will be treated under a partial (25%) reinforcement schedule. That is, patients will receive the same dose of drug previously received, but only a quarter of the daily packets will contain active drug (12.5 mg); the remaining capsules will contain only an inert substance. Packets will be arranged to ensure that a patient never receives the “placebo” for more than two consecutive times. The selection of a 25% reinforcement schedule is based on the fact that we are using the minimum recommended starting dose of , and lower doses (particularly this much lower) are likely to have minimal if any pharmacologic effect. Therefore, the total daily dose of 6.25 mg. would not be sufficient to sustain the normotensive levels achieved under continuous reinforcement during the baseline period.

Dose Control Group-1, a control for the cumulative amount of drug received by the Partial Reinforcement Group, will be treated twice daily under a continuous (100%) reinforcement schedule, but each packet will contain only 25% of the active drug received during the baseline period.

To be sure that the reduced amount of drug received by the Partial Reinforcement Group is not sufficient by itself to lower blood pressure, a **Dose Control-2 Group** will receive the same active dose as the Partial Reinforcement Group but will not receive CSs on the intervening doses (6.25 mg once every other day).

Table 1. Experimental Protocol

GROUP	BASELINE PERIOD (15 days)			EXPERIMENTAL PERIOD (15 days)		
	Drug Dose*	Reinforcement Schedule**	Freq.	Daily Drug Dose***	Reinforcement Schedule**	Freq.
Standard Therapy	25	100	2xDay	25	100	2xDay
Partial Reinforcement	25	100	2xDay	6.25	25	2xDay

RSRB: 36447 12 V08.03.2016

Dose Control-1	25	100	2xDay	6.25	100	2xDay
Dose Control-2	25	100	2xDay	6.25	100	every other day

* Daily Dosage in mg of antihypertensive medication

** Percentage of treatment occasions when active drug is received

*** Average Daily Dosage in mg of antihypertensive medication

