If, as anticipated, there are a sufficient number of patients from Experiment 1 who show no evidence of relapse within the 15-day experimental period, we can proceed to Experiment 2. The remaining patients from the Standard Therapy and Partial Reinforcement Groups (and, perhaps, the Dose Control Group-1) would be divided into two subgroups. For one subgroup, all medication would be discontinued for a period of 2-4 wk; for the other subgroup, active drug would be discontinued but the patients would continue to receive the distinctive capsules containing inert substance. It is predicted that: (a) patients reexposed to the CS will be less likely to relapse or show a slower rate of relapse than patients in groups that are not reexposed to the CS; and (b) patients in the Partial Reinforcement Group will be more resistant to extinction (slower to relapse) than patients remaining from Dose Control Group-1 who were treated with the same cumulative amount of drug and may even be indistinguishable from the Standard Therapy Group that had received three times more drug. An alternative strategy, of course, would be to enlist a new population.

c) Statistical Analysis: Data analyses are described separately for each of the specific hypotheses. All statistical tests will be two-sided with $p \leq .05$. The principal analyses focus on the difference over 2-weeks between PR and two dose control groups (DC-1 and DC-2) in Experiment 1. The main independent variable is time to relapse as well as symptom reduction (blood pressure). These two outcomes will also be examined in Experiment 2 to see if they differ between the two groups (placebo and no-treatment groups). Because power for the comparisons in the second experiment may be undercut by high relapse rates in the first experiment, this second set of analyses is exploratory.

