- b) **Potential Risk:** Low risk of transient low blood pressure. Subjects may have treatment for stage I hypertension delayed during the short duration of the study, but this is similar to approach that many newly diagnosed hypertensive patients receive (several months of attempts at non-pharmacological Therapy)
- c) **Protection against risks:** Close monitoring by investigators, Drs. [name] and [name] will function as patient safety monitors as part of the study team ii) Data Safety Monitoring Board Meeting every 6 months.
- d) **Potential Benefit to Subjects:** none
- e) **Alternatives to Participation:** standard treatment of hypertension.

V. SUBJECT IDENTIFICATION, RECRUITMENT AND CONSENT/ASSENT

Method of Subject Identification and Recruitment:

- a) Subjects will be recruited by referrals from the physicians who practice in the general medicine outpatient clinics of Strong Memorial Hospital and all affiliated clinics.
- b) The study coordinator will work in collaboration with the Greater Rochester Practice Based Research Network (GR-PBRN) executive committee to expand recruitment opportunities. The relationship will be on-going for the duration of the study to seek best methods of recruitment from primary care practices. The objective is to make the primary care physician the point of contact with regard to announcing the research opportunity for our study.
- c) On an as needed basis, the study coordinator will work with the Clinical Translational Science Institute (CTSI) Research Support Center staff at the University of Rochester Medical Center.
- d) Primary care practice lists identifying potentially-eligible participants will be sent to either the study coordinator or CTSI Support Staff; depending on the preference of the patient care practice group.
- e) If a primary practice prefers the research letters are sent through CTSI Research Support Staff, the list of potentially-eligible participants will be processed and distributed through their staff. The letter will announce the research opportunity and direct interested parties to contact the study coordinator, not the primary care physician.

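### Experiment 2 withdraws carvedilol in both subgroups but sets no review of home readings near the 3-day point at which the protocol itself says rebound could occur

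*Combined protocol and SAP*

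**What the plan says.** All references are to the combined protocol and SAP.

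- **Withdrawal.** Section III, Experiment 2, divides the remaining Standard Therapy (ST) and Partial Reinforcement (PR) patients, and perhaps those of Dose Control-1 (DC-1), into two subgroups. For one, "all medication would be discontinued for a period of 2-4 wk". The other keeps the distinctive capsules, now without drug. Under Length of study, placebo may continue past 4 weeks until relapse, and of the no-treatment subgroup the authors write "We expect the latter group to relapse after a few days".
- **Rebound.** Section III(a), item d of the reasons for choosing the drug, argues that twice-daily dosing protects patients on one active dose in four from the "undesired rebound side effects of this medication that could occur if they were to have 3 days with no active drug".
- **Monitoring.** Patients take two readings each morning and two each evening. The Schedule of Events lists diary review, vital signs and adverse events weekly. Section III, Experiment 1, lets the patient return weekly or within 14 days, and adds: "The study coordinator will email or call to check on safety of the subject in the interim of a weekly clinic visit".
- **Risk section.** Section IV(b) reads "Low risk of transient low blood pressure. Subjects may have treatment for stage I hypertension delayed during the short duration of the study". Section IV(c) adds close monitoring, safety monitors and a Data Safety Monitoring Board that meets every 6 months.
- **Aim 2 analysis.** Section III(c) carries the Aim 1 methods over to Aim 2. Under those methods a covariate enters the model only if it is found to differ between the groups.

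**The concern.** The protocol names a hazard and the condition under which it could arise, and designs Experiment 1 dosing with that in mind. It then adds a phase in which every participant meets the condition, without carrying the precaution forward. The rebound remark was written about the reduced-schedule groups of Experiment 1, but its condition is simply 3 days with no active drug.

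If a patient's pressure rose sharply in the first days, the patient's own monitor would record it, yet nothing in the plan says that anyone on the study team would look before the weekly or later visit. The relapse definition does not fill this role. It asks for three consecutive days at the enrollment value, has no upper safety limit, and works only once someone reads the diary. No blood pressure value for action and no rule for restarting treatment is given.

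ST patients are the most exposed. They go straight from 25 mg/day to nothing, whereas PR and any DC-1 patients have already spent the experimental period at an average of 6.25 mg/day.

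A smaller statistical matter sits beside this. Hypothesis 2 in Section I(a) is stated to hold whatever the initial regimen, yet prior regimen would enter the Aim 2 models only if it happened to differ significantly between the two subgroups.

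**Working it through.** The plan gives no figure to reproduce here. The check compares its own times and counts.

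**1. Timing of review.** Assume that the last active dose falls at the visit that starts Experiment 2, and that the visit flexibility described under Experiment 1 also applies in Experiment 2.

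- Point named for rebound: day 3.
- First scheduled diary review: day 7 (weekly), or day 14 at the latest.
- Delay after day 3: 7 − 3 = 4 days, to 14 − 3 = 11 days.
- Readings per day: 2 + 2 = 4. By day 3 there are 3 × 4 = 12 readings; by day 7, 28; by day 14, 56.

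So 12 readings exist by day 3, and 28 to 56 accumulate before a scheduled review. The interim contact may fall in this window, but its day and content are not fixed.

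**2. Size of the step at withdrawal.**

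- ST: 25 mg/day to 0, after up to 15 + 15 = 30 days of drug (Length of study says 4 weeks).
- PR and DC-1: an average of 6.25 mg/day to 0. The ST step is 25 / 6.25 = 4 times as large.

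**3. Reassurance from the earlier atenolol study (Section I(b)).** It reports no serious adverse outcomes among 25 participants, after one week of active drug.

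- One-sided 95% upper limit for 0 events in 25: 1 − 0.05^(1/25) = 11.3%.
- Exposure before withdrawal: 30 / 7 = 4.3 times longer here for ST patients.

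The study is reassuring, but it cannot exclude a serious-event rate of up to about 11%, and it used another drug for a shorter time.

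**4. Aim 2 covariate rule.** Assume an equal split into two subgroups that is not made within Experiment 1 groups. The number of ST patients in a subgroup is then hypergeometric.

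| Patients remaining (assumed) | SD of difference in ST share | Smallest difference with chi-square p ≤ 0.05 | Splits left unadjusted |
|---|---|---|---|
| 37 ST + 37 PR | 11.7 points | 24.3 points | 94% |
| 30 ST + 18 PR | 14.1 points | 33.3 points | 96% |

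The shift in the Aim 2 hazard ratio at a 1-SD imbalance is exp(imbalance × ln HR), where HR is an assumed hazard ratio of 1.5 to 2 for prior regimen:

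- exp(0.117 × ln 1.5) = 1.05 to exp(0.117 × ln 2) = 1.08
- exp(0.141 × ln 1.5) = 1.06 to exp(0.141 × ln 2) = 1.10

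The shift is therefore a factor of 1.05 to 1.10 in either direction, averaging to no bias over splits. It largely vanishes if the split is made within groups.

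**The case against.** The best defence is context. Experiment 2 is conditional on time and on the results of Experiment 1, and is labelled exploratory, so thin operational detail is unsurprising. Patients have mild hypertension and take the lowest recommended starting dose. There are weekly visits, a safety call or email between them, safety monitors and a DSMB. The risk section does disclose delayed treatment. All of this stands and lowers the severity. None of it places a look at the readings near day 3.

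A second objection is that the choice of day 3 is clinical, and that review without an action rule protects little. That is right, and it is why the fix below includes a threshold.

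A reader might also infer more than the documents support:

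- **That Experiment 2 multiplies the drug-free gap many times over Experiment 1.** Such a ratio would take the longest PR gap from the rule that "the patient would receive no more than two doses of consecutive placebo capsules". That rule cannot hold on a 25% schedule: over 30 capsules, 8 active doses leave 9 slots × 2 = 18 placebos, but 22 are needed. A 25% schedule taken twice daily averages 48 hours between active doses. A longer gap beyond day 3 also says nothing more about rebound.
- **That the endpoint is compromised.** Readings are recorded four times a day whenever they are reviewed, so an early relapse can be dated afterwards.
- **That participants were not told of rebound.** The consent pages are not in the published document, so this cannot be judged.

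**Conclusion.** The point holds as a gap in safety planning, of moderate weight. On the protocol's own account rebound could occur with 3 days of no active drug. Both Experiment 2 subgroups reach that state, and the first scheduled review of readings comes 4 to 11 days later. The upper figure rests on the visit flexibility applying in Experiment 2, and both rest on the last active dose falling at the start visit. Existing safeguards narrow the gap without closing it. The documents give neither the frequency nor the size of rebound, so they do not support a claim that patients would be harmed or that withdrawal is unsafe in itself.

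The Aim 2 matter is minor. It would be tempting to call the unadjusted comparison biased, but under random division it is not biased on average. Prespecified adjustment removes chance imbalance in prior regimen and fits hypothesis 2. The likely effect is small and depends on the assumed hazard ratio and on how the split is made.

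**What to change.** For Experiment 2:

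1. Hold the existing interim contact at about day 3 after the last active dose, on the same day in both subgroups so that contact does not differ between them. The exact day is for the clinicians to set.
2. Have that contact review the home readings already collected.
3. Attach a clinician-set blood pressure or symptom threshold for restarting treatment, and state how a restart before formal relapse is handled in the time-to-relapse analysis.
4. Name rebound on withdrawal in Section IV(b).

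For the Aim 2 analysis, stratify the Cox model by Experiment 1 group and enter that group as a fixed effect in the mixed model, whether or not it differs significantly between subgroups.

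The cost is a fixed contact date, a short checklist with an agreed threshold, one line in the risk section and one model term for a factor already recorded. No new visits or measurements are needed.

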b) Number of Subjects: 121. Sample size and Power Analysis: The proposed study will recruit 37 subjects for each of the ST, PR and DC1 treatment conditions, and 10 subjects for the CD2 group. The study has 93% power to detect a 50% difference in relapse rate between group 2 and group 3 over the 2-week assessment period, even account for 10% dropout rate based on a two-sided $\alpha = 0.05$ using the method of Lakatos, E. (35). We selected a 50% relapse rate difference for the power calculation based on our prior experience. For the primary continuous symptom measure blood pressure, we have 80% power to detect about a medium effect size 0.56 based on a longitudinal study design with 7 assessment points, a conservative estimate of within-subject correlation 0.5, and a two-sided type I $\alpha=0.05$ using the method of Tu et al. (36). Note that although blood pressure is assessed twice daily in Experiment 1, we conservatively set the number of assessments at 7 to improve the robustness of the power estimates. Thus, the proposed sample size not only has sufficient power to detect a clinically meaningful difference in relapse rates, but also to find meaningful change patterns for blood pressure over the treatment course.

c) Sex of subjects: The male to female ratio will follow the distribution of hypertension in the Rochester area community. Pregnant or nursing females will be excluded due to the nature of the intervention (carvedilol is Category C). Females of child bearing potential will be required to use 2 birth control methods during the study in order to participate.

d) Age of Subjects: 18 to 80 years of age. Carvedilol is not intended for use in children.

e) Racial and Ethnic Origin: No restrictions. It will follow the distribution of patients seen in the Rochester area.

f) Vulnerable Subjects: None will be enrolled.

III. METHODS AND PROCEDURES

a) **Study Design.** Randomized, single blind.

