The primary outcome measure will be the incidence and rate of “relapse,” defined as a blood pressure level that has risen to the baseline value (blood pressure value of the participant at the time of enrollment) for three consecutive days.

If, over the course of 15 days there is evidence of a gradual recurrence of symptoms, the experimental period can be extended. If there is no evidence of impending relapses, there are two options: (a) we can reduce the partial reinforcement schedule from 25% to 15%, for example, and adjust the dose of in the Dose Control Groups accordingly; or (b) proceed to a study of extinction effects (Experiment 2).

Timeline estimate. We propose a start-up period of 6 mo. (formulation of Consent Form, IRB approval of protocol, preparation of study personnel, data management procedures, preparation and placing of advertisements for study subjects, etc). Including an instructional session and testing of blood pressure measurements from the monitors provided to patients, patients enrolled in the study could be engaged for as many as 50-60 days. We calculate being able to process 40 patients/year. A final 6 mo. would be devoted to data processing and manuscript preparation and, thus, a total project period of 4 years.

Experiment 2. *Effects of CS exposure on the persistence of drug effects following the withdrawal of drug and the effects of partial schedules of pharmacotherapeutic reinforcement on resistance to extinction.*

Based on the time available and the outcome of Experiment 1, we may be able to gather additional preliminary data on the extinction of conditioned pharmacotherapeutic effects, adding evidence that results obtained in Experiment 1 are, in fact, the results of conditioning. We expect that patients in Dose Control Group-II from Experiment 1 will relapse within 2-3 days of the treatment imposed during the experimental period. A large percentage of Dose Control Group-I patients are also expected to relapse under a reduced dose of active drug during the experimental period. However, we expect that a significant percentage of patients in the Partial Reinforcement Group (as well as the Standard Therapy Group) would be available for further study of extinction effects.

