The Cox proportional regression model will be used to examine the time to relapse outcome, while mixed-effects (MM) model will be used to compare differences in symptom reductions over time across the treatment groups. The MM approach employed for longitudinal data analysis provides valid inference under the missing at random assumption (MAR), provided that the parametric distribution assumptions are met. The MAR model is quite general, accommodating almost all missing data mechanism that may arise in practical studies (37,38). However, in the presence of missing data, estimates in both cases may be biased if the data fails to follow the assumed statistical distributions, even with the use of the sandwich variance estimates (39). In cases where distribution assumptions are seriously violated, for example, if discrepancies between the MM and WGEE for fixed-effects show very different results, we will use clustered bootstrap methods for inference (40).

Experiment 1

AIM 1: a) PR will be more effective than DC-1 and DC-2 in reducing relapse rates. PR will have similar effectiveness to ST in reducing relapse rates.

Survival analysis will be conducted using Cox proportional hazards model. We will include dummy variables for the four treatment groups in addition to the covariates found to significantly differentiate the groups at baseline. Appropriate linear contrasts will be constructed to compare PR vs. each of the dose control groups, if a significant group difference is found.

Note that to formally confirm the equivalence between PR and ST, we must use non-inferiority tests. However, since the acceptable margin of tolerable difference is difficult to define due to the lack of insufficient literature on this topic, we will not conduct such a formal analysis. The effect size will provide similar indications of treatment difference.

b) PR will have higher (similar) symptom reductions than DC-1 and DC-2 (ST).

Longitudinal methods will be applied to compare the outcomes of pruritus and biologic measures across the four groups as well as the appropriate pairwise comparisons. We will dummy code the treatment conditions, include time and time by treatment interaction in addition to the covariates found to differentiate

the four groups at baseline. The hypothesis will be supported if a significant time by treatment interaction is found. Appropriate linear contrasts will be performed to compare PR vs. DC-1, DC-2 and ST.

Experiment 2

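### Covariates are chosen by testing for baseline differences instead of being named in advance, so enrolment and randomisation blood pressure will usually drop out of the relapse model whatever their prognostic value

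*Combined protocol and SAP*

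**What the plan says.** Section III. c), Aim 1(a), sets the covariates for the Cox model of time to relapse: "We will include dummy variables for the four treatment groups in addition to the covariates found to significantly differentiate the groups at baseline". Aim 1(b) applies the same kind of rule to the mixed model, "in addition to the covariates found to differentiate" the four groups, but without requiring significance. Neither aim lists candidate covariates or names the baseline test. The reference to Aim 1 methods under Aim 2 carries the rule into Experiment 2, which the plan calls exploratory.

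Three other parts of the plan bear on this:

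- **Outcome (Experiment 1, primary outcome).** Relapse is "defined as a blood pressure level that has risen to the baseline value (blood pressure value of the participant at the time of enrollment"), held for three days in a row.
- **Entry to randomisation (Experiment 1).** "Those who satisfy the criterion of a 10-point decrease in blood pressure for a period of 5 days will be assigned randomly". No upper limit is put on the fall.
- **Allocation (section III, Medication).** "Randomization will be performed by the research pharmacy in blocks of eight". No stratification factor is given.

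The deciding tests are also stated. For relapse: "Appropriate linear contrasts will be constructed to compare PR vs. each of the dose control groups, if a significant group difference is found". For blood pressure over time: "The hypothesis will be supported if a significant time by treatment interaction is found".

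**The concern.** A baseline test in a randomised trial asks whether chance produced a difference. It does not ask whether the variable predicts the outcome, and only the second property makes a covariate useful in a Cox model. The rule therefore keeps or drops a variable without regard to its value.

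This matters more here than in most trials. Enrolment pressure is the relapse threshold, and pressure at randomisation fixes each patient's distance from it. If that distance predicts time to relapse, leaving it out pulls the estimated hazard ratio towards 1 and costs power in the principal comparison of Partial Reinforcement (PR) with Dose Control-1 (DC-1).

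The primary model also cannot be written down before the baseline data are seen. The test is unnamed, the mixed-model threshold is undefined, and the plan uses the word baseline both for enrolment and for the on-drug run-in.

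**Working it through.** **Inputs from the plan.** 37 patients in each of Standard Therapy (ST), PR and DC-1, and 10 in Dose Control-2 (DC-2); 10% dropout, so 37 × 0.9 ≈ 33 and 10 × 0.9 = 9; two-sided alpha 0.05; 15 days of follow-up. **Not in the plan:** the relapse rates, and how strongly blood pressure predicts relapse. Both are varied below.

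**1. The plan's own figure.** Section II. b) states: "The study has 93% power to detect a 50% difference in relapse rate between group 2 and group 3 over the 2-week assessment period". No control rate is given, so I used Schoenfeld's formula with 33 per arm: power = Φ(½·√events·|ln HR| − 1.96), where HR = ln(1 − p1)/ln(1 − p2).

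- 40% vs 80%: events 33 × 1.2 = 39.6, HR 0.317, power 95%.
- 39% vs 78%: power 93.5%.
- 30% vs 60%: events 33 × 0.9 = 29.7, HR 0.389, power 73%.

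The stated 93% fits a halving from just under 80%. Other readings do not fit: an absolute 50-point difference gives at least 99%, and a hazard ratio of 0.5 gives 43–81% over control rates of 50–100%.

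**2. How often the rule drops blood pressure.** With one four-group test at 5%, each value is dropped with probability 1 − 0.05 = 95%. Two independent values would both be dropped in 0.95² = 90%; with an assumed correlation of 0.5–0.7, simulation at 37/37/37/10 gives 91–92%. If any of the six pairwise tests counts, the rates are about 80% for each and 67–69% for both. None of these depends on prognostic value.

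**3. Power for PR vs DC-1, one covariate.** Simulated four-arm trials (33/33/33/9) with exponential relapse times censored at day 15. Marginal relapse was the lower rate in PR and ST and the higher rate in DC-1 and DC-2. The Wald test was used, with 8,000 trials per setting and the four-group selection test.

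| Covariate log-HR per SD | 30% vs 60%: plan / pre-specified | Gain | 40% vs 80%: plan / pre-specified | Gain |
|---|---|---|---|---|
| 0 | 70.7 / 70.7 | 0.0 | 94.8 / 94.8 | 0.0 |
| 0.25 | 71.2 / 72.4 | 1.2 | 94.7 / 95.3 | 0.6 |
| 0.5 | 71.2 / 76.5 | 5.3 | 95.4 / 97.7 | 2.3 |
| 1.0 | 72.4 / 89.2 | 16.8 | 96.3 / 99.9 | 3.6 |

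Under the any-pairwise rule the gains are 0–14 and 0–3 points. If the contrast is tested only after a significant overall test, as Aim 1(a) requires, plan / pre-specified power runs from 64.1/64.3 to 66.3/87.0 at 30% vs 60%, and from 94.0/93.9 to 95.7/99.8 at 40% vs 80%.

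**4. Both pressures included, distance to threshold prognostic** (4,000 trials per setting, correlation 0.5 or 0.7). For log-HR 0.25 to 1.0 the gain is 1 to 17 points at 30% vs 60%, and 0.3 to 4 at 40% vs 80%. If neither value is prognostic, power changes by 0 to −0.4 points.

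**5. Where the gain comes from.** At log-HR 0.5 and 30% vs 60%, the standard error does not fall (0.392 unadjusted, 0.397 adjusted). The estimated treatment log-HR rises from 0.96 to 1.05. The ratios are 0.96/0.392 = 2.45 and 1.05/0.397 = 2.64, which correspond to roughly 69% and 75% power, in line with the table.

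**6. Type I error** with 50% relapse in all groups: 4.4–5.0% under the plan's rule and 4.8–5.9% pre-specified (Monte Carlo SE 0.24–0.34 points).

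**7. Aim 1(b).** The deciding test is on change over time. Covariates entered as main effects do not sharpen it: the SD of the PR–DC-1 slope difference was 0.0330 unadjusted and 0.0332 adjusted in simulation.

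**The case against.** The strongest reply is that little is lost. The 93% rests on a log-rank method with no covariate mentioned, so the plan gives up nothing it promised; the shortfall is against a better analysis. That stands. In the scenario nearest the stated power the gain is at most about 4 points.

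Prognostic strength is not established either, and this also stands. In a check built on the relapse definition (assumed daily SD 5 mmHg; fall beyond 10 points half-normal, scale 4 or 8), distance to the threshold was prognostic at log-HR 0.35–1.26 per SD when the rise on reduced drug was unrelated to the initial fall. It was about 0 when the rise was proportional to that fall. The documents cannot tell these apart.

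Part of the gain is test calibration, because the unadjusted test is slightly conservative. At equal size, in a two-covariate check at 30% vs 60%, the gain fell from 1.1 points to about 0 at log-HR 0.25, from 5.7 to 4.4 at 0.5, and from 16.1 to 14.8 at 1.0.

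Conditional and marginal hazard ratios are different quantities, so attenuation is not bias in the usual sense. The rule is also written in advance and blind to outcomes, and it does adjust when chance imbalance is large.

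These points limit the size of the problem but do not defend the rule. The plan's wording does not forbid other covariates, yet nothing in it brings any in.

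**Conclusion.** The concern holds, as an efficiency and specification problem and not as a threat to validity. The rule drops each blood pressure value in about 95% of trials (80% if any pairwise test counts), whatever its link with relapse.

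The power cost for PR vs DC-1 depends on two quantities the plan does not give. It is nil if blood pressure is not prognostic and about 1 point at log-HR 0.25 per SD. It reaches about 17 points only at 30% vs 60% relapse with a hazard ratio of e^1.0 = 2.7 per SD, which nothing in the documents supports. Near the stated 93% power the loss is a few points at most. Fixing the conditional hazard ratio at 0.5 instead, with 70% relapse in the dose controls, gives larger losses (52% vs 58% at log-HR 0.5; 38% vs 60% at 1.0), but from a base power of about 58%, well below the plan's figure.

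No gain is claimed for the Aim 1(b) test, and no figure for Experiment 2. The change should be made because it makes the primary model determinate at almost no cost.

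**What to change.** In section III. c), Aims 1(a) and 1(b):

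- Delete the rule that selects covariates by baseline difference.
- In the Cox model, pre-specify enrolment blood pressure and blood pressure at randomisation (mean over the qualifying 5 days) as covariates, whatever the baseline comparison shows. Use the pressure component that defines relapse, and state which one it is, since the relapse definition does not.
- Put the same two covariates in the mixed model. This gives the deciding test no extra power, but it removes an undefined threshold.
- Keep the planned time-by-treatment test and the PR contrasts with DC-1, DC-2 and ST.

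The cost is SAP wording. Both values are already needed to apply the randomisation criterion and to judge relapse. The model spends one or two degrees of freedom, and the hazard ratio becomes conditional on these pressures, which the report should say. If blood pressure turns out not to be prognostic, power changes by 0 to −0.4 points.
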